11.3. SAS Code for Dose Response Modelling

We utilize SAS code from the chapter on Classical Dose-Response Study from *Modern Approaches to Clinical Trials Using SAS®: Classical, Adaptive, and Bayesian Methods* edited by Sandeep M. Menon and Richard C. Zink (page 185). We assume the data set data1 contains the response for each dose and use arbitrary initial values for demonstration purposes.

```
*** Sigmoidal E_max model;
proc nlmixed data=data1 alpha=0.05;
  *** set up initial values
  parms e0=10 emax=80 ed50=5.5 h=1 v=400;
  *** Specify that ed50 must be positive;
  bounds ed50>0;
  *** Define model;
  if dose=0 then eta = e0;
  else eta = e0 + (emax*dose**h) / (ed50**h+dose**h);
  model resp ~ normal(eta, v);

  *** Estimate the difference in means;
  estimate "Diff Means (dose 2400 mg – placebo)"
    e0+((emax*2400**h)/(ed50**h+2400**h))-e0;
  estimate "Diff Means (dose 1200 mg – placebo)"
    e0+((emax*1200**h)/(ed50**h+1200**h))-e0;
  estimate "Diff Means (dose 600 mg – placebo)"
    e0+((emax*600**h)/(ed50**h+600**h))-e0;
  estimate "Diff Means (dose 300 mg – placebo)"
```

$e0 + ((\text{emax} * 300 ** h) / (\text{ed}50 ** h + 300 ** h)) - e0;$

predict eta out=etahat;

****output estimations;

****dataset est has output for estimate of the mean differences;

****dataset parms has output for parameters: e0 emax ed50 h;

ods output AdditionalEstimates=est ParameterEstimates=parms;

run;

*** Hyperbolic E_max model;

proc nlmixed data=data1 alpha=0.05;

*** set up initial values

parms e0=10 emax=80 ed50=5.5 v=400;

*** Specify that ed50 must be positive;

bounds ed50>0;

*** Define model;

if dose=0 then eta = e0;

else eta = e0 + (emax*dose) / (ed50+dose));

model resp ~ normal(eta, v);

*** Estimate the difference in means;

estimate "Diff Means (dose 2400 mg – placebo)"

$e0 + ((\text{emax} * 2400) / (\text{ed}50 + 2400)) - e0;$

estimate “Diff Means (dose 1200 mg – placebo)”

$e0 + ((\text{emax} * 1200) / (\text{ed}50 + 1200)) - e0;$

estimate “Diff Means (dose 600 mg – placebo)”

$e0 + ((\text{emax} * 600) / (\text{ed}50 + 600)) - e0;$

estimate “Diff Means (dose 300 mg – placebo)”

$e0 + ((\text{emax} * 300) / (\text{ed}50 + 300)) - e0;$

predict eta out=etahat;

****output estimations;

****dataset est has output for estimate of the mean differences;

****dataset parms has output for parameters: e0 emax ed50;

ods output AdditionalEstimates=est ParameterEstimates=parms;

run;

*** Linear model;

proc nlmixed data=data1 alpha=0.05;

*** set up initial values

parms e0=10 beta1=80 beta2=80 v=400;

*** Define model;

if dose=0 then eta = e0;

else eta = e0 + beta1 * dose;

model resp ~ normal(eta, v);

```
*** Estimate the difference in means;
estimate "Diff Means (dose 2400 mg – placebo)"
    e0+ beta1 * 2400 - e0;
estimate "Diff Means (dose 1200 mg – placebo)"
    e0+ beta1 * 1200 - e0;
estimate "Diff Means (dose 600 mg – placebo)"
    e0+ beta1 * 600 - e0;
estimate "Diff Means (dose 300 mg – placebo)"
    e0+ beta1 * 300 - e0;

predict eta out=etahat;
****output estimations
****dataset est has output for estimate of the mean differences;
****dataset parms has output for parameters: e0 beta1;
ods output AdditionalEstimates=est ParameterEstimates=parms;
run;
*** Exponential model;
proc nlmixed data=data1 alpha=0.05;
    *** set up initial values
    parms e0=10 e1=1 delta=1;

    *** Define model;
```

```
if dose=0 then eta = e0;
else eta = e0 + e1 * (exp(dose/delta)-1);
model resp ~ normal(eta, v);
*** Specify that delta must be positive;
bounds delta>0;

*** Estimate the difference in means;
estimate “Diff Means (dose 2400 mg – placebo)”
    e0+ e1 * (exp(2400/delta)-1) - e0;
estimate “Diff Means (dose 1200 mg – placebo)”
    e0+ e1 * (exp(1200/delta)-1) - e0;
estimate “Diff Means (dose 600 mg – placebo)”
    e0+ e1 * (exp(600/delta)-1) - e0;
estimate “Diff Means (dose 300 mg – placebo)”
    e0+ e1 * (exp(300/delta)-1) - e0;
predict eta out=etahat;
****output estimations
****dataset est has output for estimate of the mean differences;
****dataset parms has output for parameters: e0 e1 delta;
ods output AdditionalEstimates=est ParameterEstimates=parms;
run;
```

Signature Page for VV-RIM-00145959 v1.0

ESig Approval	[Redacted]
---------------	------------

ESig Approval	[Redacted]
---------------	------------

ESig Approval	[Redacted]
---------------	------------

ESig Approval	[Redacted]
---------------	------------

ESig Approval	[Redacted]
---------------	------------

ESig Approval	[Redacted]
---------------	------------

Signature Page for VV-RIM-00145959 v1.0 Approved

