5.7.1. Analysis of Primary Efficacy Variable

The primary virologic efficacy variable is the time-weighted average change from baseline in viral load from day 1 to day 7, as measured by RT-qPCR in NP swab samples. The primary analysis will be conducted in the Seronegative mFAS population. An Analysis of Covariance (ANCOVA) model with treatment group as a fixed effect and baseline viral load and treatment by baseline interaction as covariates will be fit to the data as the primary analysis. For efficacy analysis, the placebo IV and placebo SC arms are pooled.

A step-down testing approach will be used for comparing active treatment groups to the pooled placebo to control type I error rate at 0.05. The pairwise comparisons are performed using the t-

test. [Figure 2](#) below illustrates this hierarchy. If a test is insignificant, then the formal testing procedure stops at that step.

Figure 2: Testing Hierarchy

The least squares mean estimates and 95% confidence intervals for the TWA mean change from baseline in viral load will be presented for each treatment group, as well as for the difference between each REGN10933+REGN1097 treatment group and placebo along along with the p-values for the comparisons. Accompanying descriptive analyses will be provided at the individual timepoints used to calculate the TWA.

No hypothesis testing is planned for the between active dose comparisons. Only estimates and 95% confidence intervals will be reported for the between active dose comparisons.

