5.7.4. Dose Response Modelling

Several dose response models will be explored for the TWA of change in baseline in viral load (\log_{10} copies/mL) from day 1 to day 7, and then a single model is selected using Akaike's Information Criteria (AIC). The AIC considers a trade-off between increasing the number of parameters in terms of goodness-of-fit by introducing a penalty for the number of parameters. The model with the lowest AIC value is selected. The models under consideration are linear, hyperbolic E_{max} , and sigmoidal E_{max} . Additional models may be considered. As the dose response testing and modelling is for estimation, there will be no adjustment for multiplicity.

Table 4: Set of Candidate Dose Response Models

Name	Model	Description
Sigmoidal E_{max}	$y_i = E_0 + E_{max} \frac{D_i^h}{ED_{50}^h + D_i^h} + \epsilon_i$	
i: the patient ID y_i: the response for the i^{th} patient E_0: the placebo effect E_{max}: The maximum effect attributable to the drug ED_{50}: The dose that produces one-half of E_{max} h: The hill parameter and determines the steepness of the slope D_i: The dose-level for the i^{th} patient ϵ_i: The error term for the i^{th} patient where each error term is independent and identically Normally distributed with mean 0 and standard deviation σ.

Hyperbolic E_{max}	$y_i = E_0 + E_{max} \frac{D_i}{ED_{50} + D_i} + \epsilon_i$	Special case of above model where $h = 1$
Linear	$y_i = E_0 + \beta_1 * D_i + \epsilon_i$	β_1 : Linear effect term
Exponential	$y_i = E_0 + E_1 \left(\exp\left(\frac{D_i}{\delta}\right) - 1 \right) + \epsilon_i$	
E_1: Exponential term δ: Scale

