5.7.5. Analysis of Secondary Efficacy Variables

For the analysis of primary and secondary efficacy variables, the table below summarizes the quantities and corresponding methods for analysis. The details of methods are described the paragraphs that follow.

Table 5: Secondary Efficacy

Measurement	Units	Metric	Method
Viral load (D1-5)	log ₁₀ copies/mL	TWA	ANCOVA
Viral load	log ₁₀ copies/mL	Change from BL in viral load at each visit	MMRM
Viral load	log ₁₀ copies/mL	Proportions <LLOQ, <LOD, >10 ⁴ , >10 ⁵ , >10 ⁶ , or >10 ⁷	Fisher's Exact Test/Logistic Regression
Percent change in Viral Load	copies/mL	Percent change in viral load (copies/mL) to each time point	MMRM

A mixed effect model for repeated measures (MMRM) will assess the time course of treatment effect in viral load, the change from baseline in viral load (log₁₀ copies/mL) at each visit for both the Seronegative mFAS and the Overall mFAS populations. The model will include terms for baseline, treatment, visit, treatment-by-baseline interaction, baseline-by-visit interaction, and treatment-by visit interaction. Within-patient errors will be modeled with an unstructured covariance matrix; heterogeneous autoregressive (1), or compound symmetry covariance matrix will be considered in that order if a model does not converge. The least squares means estimates for the mean at each visit and mean change from baseline to each visit as well as the difference of these estimates between each anti-spike mAb treatment arm and placebo will be provided along with the corresponding standard error, p-value, and associated 95% confidence interval.

In the Seronegative mFAS, the proportion of patients who have PCR below the limit of detection (LOD), below the lower limit of quantification (LLOQ), or have qPCR levels >10⁴, >10⁵, >10⁶, or >10⁷ will be tabulated over time. The numbers of patients in each category will be tested using Fisher's Exact test. Corresponding p-values and confidence intervals will be presented.

There may be additional analysis of the proportions of patients who have PCR below the limit of detection, below the lower limit of quantification, or have quantitative PCR levels above >10⁴, >10⁵, >10⁶, or >10⁷ will be tabulated over time using logistic regression model with terms for treatment arm, baseline viral load, and the treatment-by-baseline viral load interaction. Adjusted odds ratios and corresponding p-values and confidence intervals may be estimated from the model.

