7.2. Data Handling Convention for Efficacy Variables

For efficacy variables, only observed data will be used. If the viral load is not available at the scheduled time point t_i or missing due to failed test or other reasons, only the time points with non-missing values will be included for TWA calculation. The nominal visits and results from these visits will be used to compute the TWA (the primary endpoint). Patients without a baseline will be excluded from the analysis. Additionally, patients who do not have any viral measurements during first 7 days post baseline will be excluded.

Viral loads less the lower limit of quantification of the PCR assay but with positive qualitative results will be set to half of the lower limit of quantification of the PCR assay; values with nondetectable RNA will be set to 0 \log_{10} copies/mL if the reason for the negative value is a not a failed test. Viral load values above the upper limit of quantification will be re-tested using the reflex test and the corresponding quantitative value will be used in the analysis. If two or more measurements correspond to the same visit, the “worst” value will be used. For viral load, the “worst” value is the highest. For Ct analysis, the “worst” value is the lowest value.

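### The dose-response models for the primary TWA variable leave out baseline viral load, which the primary ANCOVA for the same variable includes

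*SAP*

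**What the plan says.** SAP 5.7.4 states: "Several dose response models will be explored for the TWA of change in baseline in viral load" over days 1 to 7. The model with the lowest AIC is kept. Table 4 there lists sigmoidal Emax, hyperbolic Emax, linear and exponential models, each written as a function of the patient's dose plus an independent normal error. SAP 11.3 supplies the code. It is introduced by "We assume the data set data1 contains the response for each dose", and each of the four blocks builds the mean from dose alone, as in the linear block: "else eta = e0 + beta1 * dose".

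The other models for viral load adjust for baseline:
- SAP 5.7.1, primary ANCOVA on the same TWA variable: "baseline viral load and treatment by baseline interaction as covariates will be fit to the data as the primary analysis".
- SAP 5.7.5, MMRM: "The model will include terms for baseline, treatment, visit, treatment-by-baseline interaction, baseline-by-visit interaction".
- SAP 5.7.5, optional model for the proportions: "logistic regression model with terms for treatment arm, baseline viral load, and the treatment-by-baseline viral load interaction".

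On the status of the curves, SAP 5.7.4 says: "As the dose response testing and modelling is for estimation, there will be no adjustment for multiplicity". Protocol 11.4.3.1 likewise treats this modelling as exploratory and leaves the detail to the SAP. The SAP gives no reason for dropping the covariate.

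**The concern.** SAP 2.1 describes the purpose of the study as finding the lowest regimen whose virologic effect is close to that of 2400 mg IV. The fitted curve is the planned description of how the effect changes with dose, so its precision and the reliability of the AIC choice bear on that purpose.

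There is reason to expect baseline to predict the response. The response is a change from baseline (SAP 4.5.1), and undetectable samples are set to 0 log10 copies/mL (SAP 7.2), so no patient can fall by more than the starting value. Protocol 3.3 reports a more striking effect in the earlier study among patients with high baseline viral load. Neither passage gives a correlation, and the second describes effect modification rather than prognosis.

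A dose-only fit leaves this variation in the error term and leaves chance baseline imbalance between arms uncorrected. The curve's differences from placebo would then stand beside baseline-adjusted ANCOVA differences for the same variable, and could differ from them through imbalance alone.

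**Working it through.** **The plan's own figures.** SAP 2.2 gives a difference of -0.73, SD 0.948, 57 per group and power of about 98%. The check is 0.73 / (0.948 × √(2/57)) = 4.11, and Φ(4.11 − 1.96) = 98.4% (98.3% by noncentral t), so the figure reproduces. The half-width of 0.27 at 100 per group computes to 1.96 × 0.948 × √(2/100) = 0.263, slightly below the stated value; this does not affect the point.

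**Specification.** Baseline viral load appears in none of the four models in Table 4 and in none of the four code blocks. It appears in all three models quoted from SAP 5.7.1 and 5.7.5.

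**Theory.** With correlation r between baseline and response (assumed), residual SD = 0.948 × √(1 − r²), and the equivalent gain in patients is 1/(1 − r²) − 1.

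| r | Residual SD | Fall | Equivalent extra patients |
|---|---|---|---|
| 0 | 0.948 | 0% | 0% |
| 0.2 | 0.929 | 2% | 4% |
| 0.3 | 0.904 | 5% | 10% |
| 0.5 | 0.821 | 13% | 33% |
| 0.7 | 0.677 | 29% | 96% |

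**Simulated precision.** Assumptions: true hyperbolic Emax curve with Emax -0.75; pooled placebo and four IV arms; 57 per arm; SD 0.948; 4,000 trials per scenario. SD of the estimated 600 mg effect, without and with baseline:

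| r | ED50 50 | ED50 100 | ED50 300 |
|---|---|---|---|
| 0 | 0.1459 → 0.1464 | 0.1465 → 0.1469 | 0.1482 → 0.1489 |
| 0.2 | 0.1445 → 0.1412 | 0.1464 → 0.1441 | 0.1494 → 0.1471 |
| 0.3 | 0.1442 → 0.1382 | 0.1466 → 0.1394 | 0.1491 → 0.1436 |
| 0.5 | 0.1467 → 0.1254 | 0.1449 → 0.1243 | 0.1487 → 0.1314 |
| 0.7 | 0.1443 → 0.1028 | 0.1479 → 0.1053 | 0.1533 → 0.1113 |

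The SD rises by at most 0.5% at r = 0. It falls by 1.5 to 2.3%, 3.7 to 4.9%, 11.6 to 14.5% and 27.4 to 28.8% at r = 0.2, 0.3, 0.5 and 0.7. The 95% half-width (1.96 × SD) goes from 0.28–0.30 to 0.28–0.29, 0.27–0.28, 0.24–0.26 and 0.20–0.22 log10. Repeat runs with other random draws gave falls of 3 to 5% at r = 0.3, 9 to 15% at 0.5 and 24 to 32% at 0.7. Bias over these runs was at most 0.015 without and 0.013 with baseline, small beside the SDs.

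The gain does not depend on which arms enter the fit. With the SC arms included (seven groups of 57, ED50 150, effect -0.73 at 2400 mg), the delta-method SE of 300 mg minus placebo goes from 0.159 to 0.152, 0.138 and 0.114 at r = 0.3, 0.5 and 0.7.

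**Simulated AIC choice.** 1,000 trials per scenario, all four candidates, truth hyperbolic Emax. Entries are without / with baseline:

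| r | Correct model, ED50 100 | Correct model, ED50 300 | Linear wrongly chosen, ED50 300 |
|---|---|---|---|
| 0 | 93.2 / 93.2% | 78.2 / 78.0% | not reported |
| 0.2 | 93.2 / 93.3% | 80.6 / 80.3% | 11.5 / 11.1% |
| 0.3 | 93.5 / 94.4% | 79.2 / 80.4% | 13.5 / 11.7% |
| 0.5 | 94.8 / 95.5% | 77.7 / 85.4% | 14.4 / 6.3% |
| 0.7 | 93.4 / 95.3% | 77.5 / 88.6% | 13.7 / 2.6% |

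**If the baseline slope differs between placebo and active arms.** 3,000 trials each; slopes in SD units, placebo/active. A main-effect baseline term lowers the SD by 5.0 to 5.8% (-0.3/-0.5), 15.3 to 16.9% (-0.5/-0.7) and 8.2 to 9.1% (-0.5/-0.2), with bias of at most 0.009.

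**The case against.** The strongest reply is that this is a preference, not an error. Dose-only curves are a legitimate marginal description in randomised arms, and the SAP takes them openly from a cited text. The plan does not adjust everything: the named test for the proportions in SAP 5.7.5 is an unadjusted Fisher's exact test. SAP 5.7.1 already gives baseline-adjusted estimates for each arm and intervals between active doses, so the dose question can be answered without the curve. SAP 5.7.4 also leaves room for additional models.

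Most of this is true and limits the weight of the point. It does not give a reason to leave the covariate out of a model for the variable that the primary analysis adjusts. Room for additional models is not a specification, and adding baseline after seeing the data would be a data-dependent choice.

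Two further objections stand in full. The gain rests on an unknown r, and at 0.2 to 0.3 it is only 1.5 to 4.9% in SD. The AIC benefit is not general: at ED50 100 correct selection improves by at most 1.9 points at any r tried, and at ED50 300 with r of 0 or 0.2 it is 0.2 to 0.3 points lower.

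**Conclusion.** The concern holds, as a minor point about precision. All four dose-response models omit a covariate that the primary analysis of the same variable includes. There is no material bias, no effect on the type I error rate and no change to the ANCOVA results. The gain from adjustment runs from nothing at r = 0 to a little over a quarter of the SD at r = 0.7, and the documents do not say where r lies. A better AIC choice is supported only for r of 0.5 or more with an ED50 as high as 300.

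The absolute half-widths treat 0.948 as an unadjusted SD, which the documents do not state. If it is already adjusted for baseline, the percentages are unchanged and the half-width goes from about 0.33 (r = 0.5) or 0.40 (r = 0.7) to about 0.29. Emax, the ED50 values and r are all assumptions.

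**What to change.** Add centred baseline viral load to every candidate in Table 4 and in the SAP 11.3 code, for example eta = e0 + b × (base − meanbase) + dose term, and compare AIC only among models that contain it. Keep the dose-only fit as a sensitivity analysis if wanted. State in the SAP that this main effect does not reproduce the treatment-by-baseline interaction in the ANCOVA.

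The cost is one parameter per model. No patients are lost, since SAP 7.2 already provides: "Patients without a baseline will be excluded from the analysis". If baseline turns out not to predict the response, the price is the rise of at most 0.5% in SD shown for r = 0.

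A separate clarification, which adds nothing to the precision argument, is to state which arms data1 holds, since the dose labels in the code carry no route. Pooled placebo with the four IV arms of the Seronegative mFAS would fit the rule in SAP 2.1 and 3.1 against pooling active groups, with the SC arms reported from the ANCOVA.

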#### 3.2. Rationale

##### 3.2.1. Rationale for Study Design

In an ongoing study in outpatients with COVID-19 (R10933-10987-COV-2067; hereafter COV-2067), interim phase 1/2 and primary phase 2 analyses found that patients treated with 2400 mg or 8000 mg of REGN10933+REGN10987 IV single dose had a greater reduction in viral load compared with those who received placebo. These virologic effects translated into clinical benefit, significantly reducing COVID-19-related MAVs in these patients (with MAV defined in the study as hospitalization, emergency room visit, urgent care visit, physician's office visit, or telemedicine visit, with the primary reason for the visit being COVID-19). Notably, virologic and clinical efficacy were similar among those treated with either 2400 mg or 8000 mg, suggesting that maximal benefit may have already been reached at the 2400 mg dose (refer to the Investigator's Brochure for more information on these analyses).

This randomized, double-blinded, placebo-controlled, parallel group study (R10933-10987-COV-20145) will assess the virologic efficacy, as well as safety and tolerability, of REGN10933+REGN10987 at different single dose regimens in outpatients with SARS-CoV-2 infection. The purpose of this study is to identify a lower dose regimen capable of demonstrating the same (or similar) virologic efficacy seen at the 2400 mg IV single dose level in outpatients with COVID-19. These data, taken together with data on the safety profile of REGN10933+REGN10987 and any correlation between virologic and clinical efficacy at 1200 mg, 2400 mg, and 8000 mg IV doses observed in Study COV-2067, will aid in identifying a dose regimen with the optimal risk-benefit profile in this patient population. Moreover, identifying lower doses that are capable of reducing viral load will bolster the ability to provide therapeutic doses of REGN10933+REGN10987 in the setting of a global pandemic, where supplies of therapeutic agents are increasingly limited as caseloads rise.

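### The sigmoidal Emax code in SAP 11.3 bounds ED50 but not the Hill exponent, so a near-flat dose response can be fitted, and sometimes selected, as a reversed curve

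*SAP*

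**What the plan says.** SAP 5.7.4 plans several dose-response models for the day 1-7 TWA change in viral load, with the lowest AIC deciding the one reported. Table 4 lists sigmoidal Emax, hyperbolic Emax, linear and exponential. For the sigmoidal model E0 is the placebo effect, Emax the largest effect due to drug, ED50 the dose giving half of Emax, and h is "The hill parameter and determines the steepness of the slope". No sign is stated for h.

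SAP 11.3 gives the code. The sigmoidal block has the comment "Specify that ed50 must be positive", then "bounds ed50>0" and no bound on h, whereas the exponential block does bound its scale parameter delta above zero. Placebo is handled by its own branch, "if dose=0 then eta = e0". The printed starting values are "parms e0=10 emax=80 ed50=5.5 h=1 v=400", and the SAP says that it will "use arbitrary initial values for demonstration purposes". It gives no rule for choosing the real ones or for trying more than one.

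On the expected shape, Protocol 3.2.1 describes similar efficacy at 2400 and 8000 mg, "suggesting that maximal benefit may have already been reached at the 2400 mg dose". SAP 2.1 states the aim of finding the lowest regimen with the same or similar virologic efficacy as 2400 mg IV.

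**The concern.** The sigmoidal term can be written 1 / (1 + (ED50/D)^h). At h = 0 it equals 1/2 at every dose, so nothing in the likelihood stops the fit passing from positive to negative h. Below zero the curve reverses. Because placebo is set in a separate branch, the fit still runs: it sits at E0 for placebo, jumps towards E0 + Emax just above dose zero, then drifts back towards E0 as dose increases. That is not the model Table 4 describes.

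The other three candidates are monotone from placebo (ED50 and delta are bounded), so only the sigmoidal one can do this. What is at stake is the single reported curve in a study meant to show how much effect is lost at lower doses. A reversed curve would present 300 mg as better than 2400 mg because of noise in the arm means.

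**Working it through.** **Inputs.** Effect -0.73 and SD 0.948 log10 copies/mL (SAP 2.2). Per-group n of 57 (400/7) or 100 (700/7), from SAP 2.2. IV doses 300, 600, 1200 and 2400 mg, with pooled placebo the same size as one active arm (2:2:2:2 and 1+1, SAP Table 1). Assumptions not in the documents: IV arms only (SAP 5.7.4 does not say whether SC doses enter the fit), and the true shape of the curve.

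**The plan's own figures.** Power for 57 versus 57, difference 0.73, SD 0.948, two-sided 0.05: 98.4%, matching the stated ~98%. Between-dose 95% half-width at n = 100: 1.96 x 0.948 x sqrt(2/100) = 0.263, close to the stated 0.27. At n = 57: 1.96 x 0.948 x sqrt(2/57) = 0.348.

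**What the sign of h does.** Take ED50 = 1000 mg for illustration. With h = +1 the fraction of Emax is 1/(1 + 1000/300) = 0.23 at 300 mg and 1/(1 + 1000/2400) = 0.71 at 2400 mg. With h = -1 it is 1/(1 + 300/1000) = 0.77 and 1/(1 + 2400/1000) = 0.29.

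**Why about half under flatness.** The doses double at each step, and 300 x 2400 = 600 x 1200 = 720,000. Replacing D by 720,000/D, ED50 by 720,000/ED50 and h by -h leaves (ED50/D)^h unchanged. Reversing the dose order therefore maps every h > 0 fit to an equally good h < 0 fit. If the true effect is the same at all four doses, neither sign is favoured.

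**Simulation, flat effect of -0.73.** 2000 trials per scenario, sigmoidal maximum found over a grid of ED50 and h, AIC parameter counts 3 (linear), 4 (hyperbolic), 4 (exponential), 5 (sigmoidal).

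- Best sigmoidal fit has h < 0: 48-51% over repeated runs, at either n.
- Reversed sigmoidal is the AIC choice: 11.3-12.5%. Monte Carlo standard error is about sqrt(0.12 x 0.88/2000) = 0.7 percentage points.
- When it is chosen, 300 mg is fitted better than 2400 mg by a median of 0.28 (n = 57) or 0.21-0.22 (n = 100). Against the planned effect, 0.28/0.73 = 38% and 0.21/0.73 = 29%. Both medians lie inside the half-widths above.
- With h > 0 imposed, reversed sigmoidal fits fall to 0% and a sigmoidal is chosen in about 1%.

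**Simulation, hyperbolic truth with -0.73 at 2400 mg (n = 57 / n = 100).**

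| True ED50 (assumed) | Best sigmoidal fit has h < 0 | Reversed sigmoidal chosen by AIC |
|---|---|---|
| 10 mg | 44.5% / 43.1% | 9.9% / 9.0% |
| 50 mg | 29.1% / 23.0% | 5.6% / 3.8% |
| 100 mg | 17.1% / 10.4% | 2.4% / 1.3% |
| 300 mg | 2.7% / 0.2% | 0.3% / 0.0% |

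Other runs gave 4.9% / 4.3% chosen at 50 mg and 1.1% / 0.8% at 150 mg, and a further run gave 0.3-4.5% across 50-150 mg. About 0.3-5% is a fair summary for that range; the 5.6% cell lies just above it.

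**Starting values.** With generic quasi-Newton optimisers on flat data, the sign of h at convergence changed with the start, mainly with the ED50 start. This is a qualitative result and SAS was not used.

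**The case against.** Much of the case on the other side stands.

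- **Flatness.** A reader might infer that the sponsor expects a flat response over 300-2400 mg. The documents do not say so. Protocol 3.2.1 and 3.2.2 report flatness for 2400 versus 8000 mg only, and 3.2.2 gives the purpose here as characterising the dose-response relationship. Its forecast that antibody in lung fluid stays above either EC99 for at least 6 days at every IV dose makes a shallow curve plausible, no more.
- **Half the time.** A reader might infer that half of the reported curves would be upside down. The half describes the sigmoidal candidate under exact flatness; SAP 5.7.4 reports only the AIC choice, where the share is about 11-12%.
- **Starting values.** Percentages are not dependable. For a start at ED50 = 300 and h = 1, one optimiser set-up reached h < 0 in 3% of datasets and another in 50-55%. Opposite directions from the same data also require someone to accept a fit short of the maximum.
- **Visibility.** The reversal is not concealed: the code outputs h and all four dose-minus-placebo differences.
- **Template code.** The SAP takes the code from a textbook, with starting values that are plainly not on a log10 viral-load scale, so it must be adapted before use. But h has no stated sign in Table 4 either, so adapting the code would not necessarily supply one.
- **Consequence.** The modelling is for estimation. The ANCOVA, the step-down tests and the between-dose estimates and intervals do not depend on it.

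What remains is that the code admits a curve that contradicts Table 4, that nothing in the plan says what to do if it is fitted, and that a response near flat is a case the trial's aim has to allow for.

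**Conclusion.** The point holds as a small, cheap correction to an exploratory analysis. The missing bound is plain from the text and needs no simulation. Its effect on the reported model depends on the true curve: about 11-12% of trials under an exactly flat response, about 0.3-5% with a true ED50 of 50-150 mg, and close to nil at 300 mg. These figures assume IV arms only, equal groups of 57 or 100, SD 0.948 and a sigmoidal fit taken at its true maximum. The documents do not support a claim that a reversed curve is the likely result or that any confirmatory conclusion is at risk.

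**What to change.** 1. In SAP 11.3 change the sigmoidal constraint to `bounds ed50>0, h>0;` and state h > 0 in Table 4.
2. Replace the demonstration starting values with a small grid on the trial's own scale (for example ED50 from below 300 to 2400 mg and h from 0.5 to 4, with E0 and Emax near the observed arm means), and keep the fit with the highest likelihood.
3. Add a boundary rule: if h or ED50 ends at a boundary, report the curve as flat or not identified over 300-2400 mg, do not interpret ED50 or h, and rely on the arm-level ANCOVA estimates.

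The cost is a line of code, a line in Table 4 and a short paragraph. There is a real but small downside. Under the flat scenario, a bounded grid fit (1500 trials, h from 0.01 to 20) collapsed to an essentially flat curve in about 43% of trials and went to a near-step shape (h of 12 or more) in another 14%. The bound removes reversal but not weak identifiability; ED50, h and their standard errors would often be uninterpretable, which is why step 3 is needed. A truly inverse response would then show only in the arm-level estimates, which the plan already reports.
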